### **6.2.1 Inflammatory Lesion Counts (Papules/Pustules)**

The Investigator will count the number of papules/pustules at each study visit using the following guidelines:

- Use only the face in the assessment (the whole face down from the hairline edge to the mandibular line); and
- Count one side of the face and then the other.

### **6.2.2 Non-Inflammatory Lesion Counts (Open/Closed Comedones)**

The Investigator will count the number of open and closed comedones at each study visit using the following guidelines:

- Use only the face in the assessment (the whole face down from the hairline edge to the mandibular line);
- Do not count prominent follicular markings on the nose as open comedones; and
- Count one side of the face and then the other.

### **6.2.3 Inflammatory Lesion Counts (Nodules)**

The Investigator will count the number of nodules at each study visit using the following guidelines:

- Use only the face in the assessment (the whole face down from the hairline edge to the mandibular line); and
- Count one side of the face and then the other.

### **6.2.4 Investigator Global Assessment for Acne – SUPPLEMENT III**

This assessment should be done prior to lesion count

### **6.2.5 Investigator Global Assessment for PIH – SUPPLEMENT IV**

This assessment should be done prior to lesion count and prior to PIH distribution assessment

### **6.2.6 PIH Distribution Assessment – SUPPLEMENT V**

## 6.2.4 Disease Signs and Symptoms

The Investigator will grade the current severity of erythema (disease related and/or related to retinoid use), dryness, peeling, and oiliness as per the following:

Score	Erythema	Dryness	Peeling	Oiliness
0 = Absent	No redness	None	Smooth	Normal
1 = Trace	Faint red or pink coloration, barely perceptible	Barely perceptible dryness by palpation with no accentuation of skin markings, skin desquamation (flakes) or fissure formation	Fine peeling, barely perceptible	Mild and localized
2 = Mild	Light red or pink coloration	Easily perceptible dryness by palpation with accentuation of skin markings but no skin desquamation (flakes) or fissure formation	Slight peeling	Mild and diffuse
3 = Moderate	Medium red coloration	Easily noted dryness with accentuation of skin markings and skin desquamation (small flakes) but no fissure formation	Definitely noticeable peeling	Moderate and diffuse
4 = Severe	Beet red coloration	Easily noted dryness with accentuation of skin markings, skin desquamation (large flakes) and/or fissure formation	Extensive peeling	Prominent and dense

The Investigator will interview the subject to determine the severity of pruritus and burning since the last visit; these symptoms will be graded as per the following:

Score	Description
0 = Absent	Normal, no discomfort
1 = Trace	An awareness, but no discomfort and no intervention required
2 = Mild	Noticeable discomfort causing intermittent awareness
3 = Moderate	Noticeable discomfort causing continuous awareness
4 = Marked	Definite discomfort causing continuous awareness, interfering occasionally with normal daily activities
5 = Severe	Definite, continuous discomfort interfering with normal daily activities

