# 1 GENERAL INFORMATION

## 1.1 Introduction

Acne vulgaris is a chronic disease with devastating sequela of post-inflammatory hyperpigmentation (PIH) in patients with skin of color. The treatment of PIH in acne is complicated and controversial because some treatments such as topical retinoids may cause further PIH due to irritation.

There are several studies evaluating topical retinoids as well as Azelaic acid 15% gel. There is not much information about the effect of benzoyl peroxide and clindamycin combination in acne patients with skin of color except sub-analysis from a community based study with BP 5% and clindamycin combination at AM and a topical retinoid at PM regimen.

Therefore, the use of Onexton Gel as monotherapy in acne patients with only skin of color will be a novel contribution to our knowledge base.

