# 4 SELECTION AND WITHDRAWAL OF SUBJECTS

## 4.1 Inclusion Criteria

- i. Outpatient, subjects of skin of color, age 12 or older. Female subjects of childbearing potential must have a negative urine pregnancy test result at Baseline and practice a reliable method of contraception throughout the study;

*A female is considered of childbearing potential unless she is:*

- postmenopausal for at least 12 months prior to study drug administration;
- without a uterus and/or both ovaries; or
- has been surgically sterile for at least 6 months prior to study drug administration.

*Reliable methods of contraception are:*

- intrauterine device in use  $\geq$  90 days prior to study drug administration;
- barrier methods plus spermicide in use at least 14 days prior to study drug administration; or
- vasectomized partner.

*[Exception: Female subjects of childbearing potential who are not sexually active will not be required to practice a reliable method of contraception. These subjects may be enrolled at the Investigator's discretion if they are counseled to remain sexually inactive during the study and understand the possible risks in getting pregnant during the study.]*

- ii. Facial acne vulgaris in patients with skin of color ( Fitzpatrick Type V & VI Supplement VI) characterized by the following:
  - IGA Score for acne vulgaris 3
  - IGA Score for PIH 3
- iii. Able to understand and comply with the requirements of the study and sign Informed Consent/HIPAA Authorization forms.

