## **5.2 Study Treatment**

### **5.2.1 Details of Study Treatment**

Active ingredients of Onexton are clindamycin phosphate of 10mg in 1gm and benzoyl peroxide of 37.5mg in 1gm. Inactive ingredients include water, carbomer, homopolymer type C, propylene glycol, potassium hydroxide. It is dispensed 50gm in one bottle pump.

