**4 = 31% - 40% PIH of the face**

**5 = 41% - 50% PIH of the face**

**6 = More than 50% PIH of the face**

## SUPPLEMENT VI

### FITZPATRICK SKIN TYPE CLASSIFICATION

Skin Type	Description	Examples
I	Always burns easily and severely (painful burn); tans little or none and peels.	People most often with fair skin, blue eyes and freckles; unexposed skin is pale white.
II	Usually burns easily and severely (painful burn); tans minimally or lightly, also peels.	People most often with fair skin, red or blond hair, hazel or even brown eyes; unexposed skin is pale white.
III	Burns moderately and tans about average.	Normal, average Caucasoid; unexposed skin is white.
IV	Burns minimally, tans easily and above average with each exposure; exhibits IPD (immediate pigment darkening) reaction.	People with white or light brown skin, dark eyes (e.g. Mediterranean, Mongoloids, Oriental, Hispanics, etc.); unexposed skin is white or light brown.
V	Rarely burns; tans easily and substantially; always exhibits IPD reaction.	Brown-skinned persons (e.g. Amerindians, East Indians, Hispanics, etc.); unexposed skin is brown.
VI	Never burns and tans profusely; Exhibits IPD reaction.	Black-skinned persons (e.g. African-Americans, Australian and South Indian Aborigines); unexposed skin is black or dark brown.

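### The erythema score is defined as redness from disease or retinoid use, but no retinoid is given and the study gel is not named, so gel-related redness falls outside the score if the text is read literally

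*Combined protocol and SAP*

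**What the plan says.** The grading instruction is in Section 6, under Disease Signs and Symptoms. That section carries the number 6.2.4, which is also used for the acne IGA. It reads: "The Investigator will grade the current severity of erythema (disease related and/or related to retinoid use), dryness, peeling, and oiliness". The table below it grades each sign from 0 (absent) to 4 (severe). The erythema column runs from no redness, through "Faint red or pink coloration, barely perceptible" at grade 1, to "Beet red coloration" at grade 4.

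On treatment, Section 5.2.1 states: "Active ingredients of Onexton are clindamycin phosphate of 10mg in 1gm and benzoyl peroxide of 37.5mg in 1gm". Section 1.1 presents as the novel contribution "the use of Onexton Gel as monotherapy in acne patients with only skin of color". Supplement I lists topical retinoids on the face (14 days before Visit 1), systemic retinoids (6 months before Visit 1) and isotretinoin (6 months) among medications that are restricted or prohibited during the study.

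The schedule in Section 5.1.1 has the investigator grade peeling, erythema, dryness and oiliness at Screening, at Baseline and at Weeks 4, 8 and 16. Section 8.2 provides descriptive statistics for continuous variables and frequencies for categorical ones. It has no rule specific to erythema.

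**The concern.** The parenthetical would suit a trial in which a retinoid is part of treatment. Here it points the rater to a cause that should be absent and leaves out the one that a tolerability score exists to detect. An investigator who follows the text could see redness, judge that it comes from the gel, and leave it out of the grade. Another, or the same one at another visit, could score it. The definition does not settle which is right.

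This matters because irritation is part of the trial's rationale. Section 1.1 says that "some treatments such as topical retinoids may cause further PIH due to irritation". That sentence names retinoids, not the study gel, but it explains why local irritation is worth measuring well in this population. Section 8.1 says that the pilot is meant to show trends in safety as well as efficacy. With a single open-label arm, no comparison group would expose a score that misses treatment-related redness.

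**Working it through.** The documents give no erythema rate, no rater-agreement figure and no stated result to reproduce. The check is therefore a comparison of sections, followed by a bound on scope.

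1. **What the erythema score admits.** Section 6.2.4 (Disease Signs and Symptoms) names two causes: the disease and retinoid use. The study gel is not named.

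2. **Whether retinoid use covers the study drug.** It does not. Section 5.2.1 lists two active ingredients, neither of them a retinoid, and Section 1.1 describes monotherapy.

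3. **Whether a retinoid could be present for another reason.** Supplement I restricts or prohibits them and sets wash-outs before Visit 1. The phrase might still catch residual redness from earlier retinoid use at Screening or Baseline, but it has no intended role once the gel is started.

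4. **Whether the other signs carry the same limit.** They do not. In the same sentence, dryness, peeling and oiliness have no cause attached. Pruritus and burning, graded by interview in the same section, have none either. Erythema is the only sign restricted by attribution.

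5. **Direction of any error.** Study medication is first dispensed at Baseline, so the Screening and Baseline grades contain no redness from gel supplied by the study. A literal reading can therefore only lower grades at Weeks 4, 8 and 16. Change from Baseline would then look more favourable than it was. Nothing in the wording pushes the other way.

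6. **Scope.** There are 20 subjects (Section 1.2) and 3 on-treatment visits, so at most 20 × 3 = 60 erythema gradings are exposed to the ambiguity.

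7. **Size within that scope.** The loss ranges from zero (no gel-related redness occurs, or raters disregard the parenthetical) to all gel-related redness (raters apply it strictly). The documents give nothing with which to narrow this range.

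**The case against.** The strongest reply is that the anchors grade visible colour, not cause. Grade 0 means no redness, and a rater looking at a red face cannot truthfully record that. Redness is lost only if the rater first attributes it to the gel and then discards it, and no separate instruction asks for that step. This stands as a reason to call the understatement a risk and not a fact. It does not remove the inconsistency, because the score still depends on whether the rater heeds the parenthetical.

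Second, there are other routes. Section 7.1 defines adverse events without regard to cause and counts conditions that are new or worse. Section 7.2.2 requires each event and its severity to be recorded, and Section 8.2 tabulates them. Gel-related redness thus remains reportable. This is a partial backstop, since it does not supply the 0–4 grade at each visit. Dryness, peeling, burning and pruritus are also graded without a cause restriction, and PIH itself is assessed at every visit. A wholly misleading picture of irritation is therefore unlikely to follow from this line alone.

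Third, erythema is neither a co-primary nor a secondary endpoint in Sections 6.1 and 6.2. That stands and limits the consequence to tolerability reporting.

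A reader might go further and infer that pink-to-red anchors must under-read erythema in this trial. Section 4.1 specifies "Facial acne vulgaris in patients with skin of color ( Fitzpatrick Type V & VI Supplement VI) characterized by the following", and Supplement VI says of type VI that "unexposed skin is black or dark brown". The difficulty is plausible, but no part of the documents shows that the scale has a floor effect in types V and VI. It can be noted only as a possible limitation when the erythema table is interpreted.

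Nor do the documents support re-anchoring the scale to contrast with adjacent uninvolved skin. Supplement II has the gel spread over the whole face, so diffuse redness could leave no untreated facial comparator. Counting darkening as erythema would mix it with PIH, which every subject has at grade 3 on entry and which is a co-primary outcome.

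**Conclusion.** The inconsistency is real and lies within the protocol: the erythema definition does not match the study treatment. Read literally, it excludes gel-related redness from a score collected to monitor tolerability. The effect is confined to the erythema summaries at Weeks 4, 8 and 16, at most 60 gradings. Its direction is towards understating treatment-related erythema, and its size is unknown and possibly nil. The co-primary and secondary efficacy results are not affected.

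The conclusion rests on two readings: that the parenthetical is meant as a definition and not a passing remark, and that the Supplement I listing means retinoids are not in use during treatment. A reader might infer that under-scoring will occur, or attach a percentage to it. The documents support neither, because they give no rate of gel-related erythema and no information on how raters apply the line.

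**What to change.** In the Disease Signs and Symptoms section, replace the parenthetical after erythema with *(from any cause, including the study gel)*. Apply the same rule at every visit from Screening onward, including Baseline, so that change from Baseline compares like with like. The new wording still covers disease-related redness and any residual redness from earlier retinoid use, so nothing now captured is lost.

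Leave the 0–4 grades and their anchors as they are. When the erythema table is reported, one sentence may note that red and pink shades may be harder to read in Fitzpatrick V and VI skin, worded as a possible limitation.

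The cost is one phrase in the protocol and the matching line on any rating form. No visit, assessment or analysis changes, and the wording has no evident downside.

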## 7 ASSESSMENTS OF SAFETY

### 7.1 Safety Assessments

Throughout the study, subjects will be monitored for signs and symptoms of adverse events. An *adverse event* is any pathological or unintended change in the structure, function or chemistry of the body that occurs during the study, irrespective of causality, including any illness, injury, toxicity, sensitivity, or sudden death. The condition must either not be present pre-study or must worsen in either intensity or frequency during the study.

A *serious adverse event* is any untoward medical occurrence, that, at any dose:

- results in death;
- is life-threatening;
- requires in-patient hospitalization or prolongation of existing hospitalization;
- results in persistent or significant disability/incapacity;
- is a congenital anomaly/birth defect; or
- is an important medical event.

An *unexpected adverse event* is any treatment-related adverse event, which is not identified in nature, severity, or frequency in current literature on the test product.

## **7.2 Reporting Requirements**

### **7.2.1 Serious and/or Unexpected Adverse Events**

Any serious or treatment-related unexpected adverse event occurring in this study must be promptly reported to the IRB as per its reporting guidelines.

### **7.2.2 Adverse Event Reporting**

All adverse events must be recorded by the Investigator into the CRF. The Investigator will be required to describe the adverse event, onset and stop date, severity, the course of action taken, if any, as well as any pertinent data necessary to allow a complete evaluation of the adverse event. For serious adverse events, an additional report (SAE report) must be completed.

### **7.2.3 Follow-up and Final Reports**

Subjects who have had a serious adverse event must be followed clinically until all parameters, including laboratory values (if applicable), have either returned to normal or are otherwise explained. If death was the outcome of the event on the initial SAE Report, a Follow-up/Final Report, including autopsy report, when performed, must be completed.

## **8 STATISTICS**

### **8.1 Sample Size Justification**

This is a pilot study and a formal justification for the sample size is not provided. The data from this study will provide important data for determining any trends regarding the safety and efficacy of study medication.

### **8.2 Analyses**

Statistical analyses will be conducted on an intent-to-treat basis (i.e., all enrolled subjects will be included in the analyses). All statistical tests will be two-sided and interpreted at a 5% significance level. Descriptive statistics (i.e., mean, standard deviation, etc.) will be provided for all continuous variables and frequencies for all categorical variables collected in this study. These will be presented by treatment group. Summary tables will be used to present patient population characteristics at Baseline; data from the study questionnaires will be included. The incidence and severity of adverse and/or unexpected events will be tabulated and a complete listing of all reports of adverse and/or unexpected events will be presented.

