## 1.2 Study Population

Twenty (20) subjects with skin of color who are 12 years of age or older with moderate facial acne vulgaris and moderate PIH on IGA scale

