# 3 STUDY DESIGN

This is a single-center, open label pilot study. The study is comprised of 5 study visits; Screening, Baseline, and weeks 4, 8, and 16. All subjects will receive Onexton QD at Baseline. We will evaluate Investigator Global Assessment of acne (IGA), total lesion count, inflammatory lesion count, non-inflammatory lesion count, Investigator Global Assessment of PIH and distribution of PIH, adverse events and concomitant medications.

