## **4.3 Withdrawal of Subjects**

It is the right and duty of the Investigator to discontinue the study participation of a subject when the subject's health or well-being is threatened by continuation in the study. Such subjects should be withdrawn from the study and not continued under a modified regimen.

The following are circumstances that would result in the subject's discontinuation from the study:

- the subject experiences a serious adverse event rendering them unable to continue study participation;
- the subject is unable to physically or mentally tolerate the use of the test medication;
- an exclusion criterion becomes apparent at any time during the study; or
- the subject voluntarily withdraws.

In the event of premature discontinuation from the study, the Investigator should determine the primary reason for discontinuation. A subject who is withdrawn from the study prior to initiation of treatment may be replaced.

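### Section 8.2 gives the six tolerability scores only generic summaries, with no visit denominator, no comparison with Baseline and no rule for subjects whom section 4.3 removes for intolerance

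*Combined protocol and SAP*

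**What the plan says.** The trial is small and has no control arm: "This is a single-center, open label pilot study", with a planned size in section 1.2 of "Twenty (20) subjects with skin of color who are 12 years of age or older".

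The schedule in section 5.1.1 scores tolerability at Screening, Baseline and weeks 4, 8 and 16. It has no early-termination visit. Under Disease Signs and Symptoms (the second section numbered 6.2.4), "The Investigator will grade the current severity of erythema", and likewise of dryness, peeling and oiliness, each from 0 to 4. The text there allows that erythema may come from the disease itself. Pruritus and burning are graded 0 to 5 by interview and cover the time since the last visit.

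Section 4.3 lists among the causes of discontinuation from the study that "the subject is unable to physically or mentally tolerate the use of the test medication". For subjects whose health is threatened it adds: "Such subjects should be withdrawn from the study and not continued under a modified regimen". Replacement is limited: "A subject who is withdrawn from the study prior to initiation of treatment may be replaced". On the reason for leaving it says: "In the event of premature discontinuation from the study, the Investigator should determine the primary reason for discontinuation".

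Section 8.2 does not name the tolerability scores. Its general rule is: "Descriptive statistics (i.e., mean, standard deviation, etc.) will be provided for all continuous variables and frequencies for all categorical variables collected in this study". The section also declares an intent-to-treat analysis of everyone enrolled, and it promises a tabulation of adverse events by incidence and severity with a full listing. It contains no missing-data rule, no denominator for each visit, no change from Baseline, no worst-grade summary and no table of discontinuations by reason.

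**The concern.** A subject who leaves because the gel is intolerable has no later scores, so whether a score is missing depends on what the score measures. Such a subject is not replaced, because replacement applies only before treatment starts. Section 8.2 says that everyone enrolled is analysed but gives no way to do this for someone who has gone. If the later tables are built from the scores that exist, irritation can appear to fade by week 16 partly because the irritated subjects have left.

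A second gap does not depend on withdrawals. With no control arm, the subject's own Baseline is the only comparator, and the stated summaries do not use it. A count of subjects with erythema at week 4 mixes disease signs already present with new irritation. A series of such counts also does not show how many different subjects were affected at some time.

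This matters because section 1.1 gives irritation as the reason why some acne treatments may worsen hyperpigmentation in this population, and section 8.1 says the pilot is meant to show trends in safety as well as efficacy.

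**Working it through.** The documents state no tolerability rate, withdrawal rate, effect size or power, so there is no figure of the plan's own to reproduce. All inputs below except N = 20 (section 1.2) and the three post-Baseline visits (section 5.1.1) are assumptions.

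**1. Effect of withdrawals on a week-16 percentage.** Take one score and call a subject affected if the grade is moderate or worse. Suppose all 20 are treated, d leave before week 16 because of that score, and m of those remaining are affected at week 16.

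- Observed scores only: m / (20 − d)
- All treated, each such withdrawal counted as affected: (m + d) / 20
- Gap: (m + d)/20 − m/(20 − d)

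| d | m = 0 | m = 2 | m = 4 | Gap, points |
|---|---|---|---|---|
| 0 | 0% both ways | 10.0% both ways | 20.0% both ways | 0 |
| 1 | 0/19 = 0% vs 1/20 = 5.0% | 2/19 = 10.5% vs 3/20 = 15.0% | 4/19 = 21.1% vs 5/20 = 25.0% | 3.9 to 5.0 |
| 2 | 0/18 = 0% vs 2/20 = 10.0% | 2/18 = 11.1% vs 4/20 = 20.0% | 4/18 = 22.2% vs 6/20 = 30.0% | 7.8 to 10.0 |
| 3 | 0/17 = 0% vs 3/20 = 15.0% | 2/17 = 11.8% vs 5/20 = 25.0% | 4/17 = 23.5% vs 7/20 = 35.0% | 11.5 to 15.0 |
| 5 | 0/15 = 0% vs 5/20 = 25.0% | 2/15 = 13.3% vs 7/20 = 35.0% | 4/15 = 26.7% vs 9/20 = 45.0% | 18.3 to 25.0 |

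These gaps show how far two ways of counting can differ. They are not estimates of bias, because the grade that a withdrawn subject would have had at week 16 is unknown.

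**2. How likely is at least one such withdrawal?** With per-subject risk p, the chance is 1 − (1 − p)^20. This gives 33% for p = 2%, 64% for 5%, 88% for 10% and 96% for 15%.

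**3. What by-visit frequencies cannot show when nobody leaves.**

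- Ever affected: if 3 of 20 are affected at each of weeks 4, 8 and 16, the number of different subjects lies between 3 (3/20 = 15%) and 3 × 3 = 9 (9/20 = 45%).
- Newly affected: if 5 of 20 have erythema at Baseline and 5 of 20 at week 4, the number newly affected lies between 0 (the same five) and 5 (five cleared, five new).

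**4. Drift in a worst-grade summary.** Suppose a subject's true grade is stable and correctly read at Baseline, and each of the three later readings independently has a 10% chance of being scored too high. Then 1 − 0.9³ = 1 − 0.729 = 27% of subjects would appear worsened with no drug effect. A worst-grade table should therefore not stand alone.

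**The case against.** The strongest reply is that the safety report already covers these subjects. Section 8.2 declares intent-to-treat for everyone enrolled. Section 7.1 counts an event as adverse only if it was absent before the study or has worsened, which is already a comparison with the subject's prior state. Section 7.2.2 requires all adverse events to be recorded with severity and action taken, and 8.2 tabulates and lists them. Scores recorded before a withdrawal also stay in the tables for those earlier visits. Much of this stands: irritation severe enough to end participation need not vanish from the report. But no section says when a tolerability grade becomes an adverse event, so the adverse event tables capture worsening only where it is also recorded as one. The intent-to-treat statement gives an intention without a method.

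A reader might infer that 8.2 plans a completers-only analysis and that irritation will therefore be understated. The documents do not support that. They prescribe no observed-case analysis. By-visit tables are themselves an inference from the schedule, and 8.2 does not say whether the scores are categorical or continuous (a mean of observed scores has the same weakness). Understatement also needs at least one intolerance withdrawal.

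It would also be wrong to read the gap between a week-16 percentage and a worst-ever percentage as dropout bias. The two differ even with complete follow-up whenever irritation resolves before week 16.

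**Conclusion.** The gap is real and moderate. Section 8.2 leaves the tolerability scores without a denominator, a Baseline comparison or a way to represent subjects removed under 4.3. If any subject leaves for intolerance, later summaries of observed scores can lean toward those who tolerated the gel. The direction is toward less irritation, and the documents do not allow the amount to be fixed. The illustration gives zero with no such withdrawal, about 4 to 5 points with one and 18 to 25 with five, assuming that each withdrawal is attributed to the score in question and counted as affected.

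The limits on separating new worsening from Baseline signs, and on counting subjects ever affected, hold whether or not anyone withdraws. None of this undermines a 20-subject descriptive pilot, but it weakens what the pilot can say about irritation, and the remedy is cheap.

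**What to change.** In section 8.2:

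- Name the six tolerability scores and keep their frequencies by visit, with the number of subjects present shown at each visit.
- Beside these, add for each score a shift table of Baseline grade by worst post-Baseline grade over all treated subjects, with the number whose worst grade exceeds Baseline.
- Count a subject who discontinues for local intolerance as worsened on the score or scores that led to discontinuation, not on all six. Withdrawal for burning is not evidence of worse oiliness. This rule also covers a subject who leaves between visits and whose worst grade was never recorded.
- Tabulate discontinuations by reason.
- State the downside: the worst of up to three readings against a single Baseline reading tends to overstate worsening, so the shift table is to be read together with the by-visit tables.

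The cost is one shift table per score and one table of discontinuations. The scores are already collected, and section 4.3 already asks for the primary reason for leaving. The only addition to data capture is to note, when that reason is local intolerance, which sign or symptom caused it.
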